9.4. DEFINITIONS OF EXPECTEDNESS

Expected adverse events are those which are expected to occur, according to previous clinical experience, and are listed in the SmPC. The expectedness of an SAE will be assessed by the Chief Investigator (or the CI's delegate).

9.5. REPORTING SERIOUS ADVERSE EVENTS TO ICR-CTSU

Any SAE that occurs from the time of registration and up to 28 days following the last dose of axitinib must be reported.

All SAEs should be reported to ICR-CTSU, within 24 hours of the Principal Investigator (or designated representative) becoming aware of the event, by completing the trial specific SAE forms and faxing to:

The ICR-CTSU safety desk [contact] For the attention of the A-PREDICT Trial team

All SAE forms must be completed, signed, and dated by the Principal Investigator or designated representative.

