5.6. SCREENING LOG

All participating sites will be required to keep a log of all patients with metastatic renal cell carcinoma discussed at MDT who are not immediately clinically indicated for cytoreductive nephrectomy. The information collected on the log will include:

- Date patient identified

- Screening outcome (patient approached/ineligible/accepted participation/declined participation)
- Reasons for not approaching / declining participation (if available)
- Trial ID (if applicable)

This information will be used by the TMG to monitor recruitment activity. No patient identifiable data will be sent to ICR-CTSU at this stage.

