6. CONSENT & REGISTRATION

6.1. PROCEDURE FOR OBTAINING INFORMED CONSENT

The Principal Investigator (or designated individual) should discuss the trial with potentially eligible patients, describing the purpose, alternatives, drug administration plan, research objectives and follow-up of the study. Patients will be provided with a Research Ethics Committee approved patient information sheet and consent form for review and given sufficient time and a minimum of 24 hours to consider participation in the study. Once a decision has been made to enter into the trial, a signature should be obtained from the patient to confirm consent. Consent should be obtained before any trial specific assessments prescribed by the protocol are performed.

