7. TRIAL ASSESSMENTS & DISPENSING SCHEDULE

7.1. PRE-REGISTRATION ASSESSMENTS

The following screening procedures must be performed

7.1.1. WITHIN 21 DAYS PRIOR TO TRIAL REGISTRATION:

- Medical history
- Physical examination including ECOG performance status, body weight, height, temperature, blood pressure measurement (repeated twice as per inclusion criteria), heart rate, respiratory rate
- Haematology, coagulation, glucose, renal and liver function, serum calcium and LDH
- Urinalysis for protein
- Serum Thyroid Function Tests (Free T4 and TSH)
- Pregnancy test (serum or urine), if female and of child-bearing potential
- Baseline symptom assessment (NCI CTCAE v.4)
- CT thorax, abdomen and pelvis and tumour assessment using RECIST 1.1 criteria. CT must be conducted prior to the research biopsy.
- Mandatory percutaneous biopsy of non-necrotic region of primary renal tumour under ultrasound or CT guidance (see Appendix B Translational research studies)
- If possible, percutaneous biopsy of one metastatic site under ultrasound or CT guidance (see Appendix B Translational research studies).
- Histological confirmation of metastatic renal cell carcinoma from either site (if not previously confirmed)*.
- Assessment of concomitant medications

*NB If a patient consents to donate research biopsies but is subsequently found to be ineligible, these research biopsies should be notified to ICR-CTSU as described in Section 19.4.1 of the protocol: Tracking of baseline samples for ineligible patients

7.2. BASELINE ASSESSMENTS – PRETREATMENT DAY 1 WEEK 1

The following must be performed on **day 1 week 1** prior to starting the study drug unless conducted within previous 7 days as part of pre-registration assessments:

- Physical examination including ECOG performance status, body weight, temperature, blood pressure, heart rate, respiratory rate
- Haematology, coagulation, glucose, renal and liver function, serum calcium and LDH
- Urinalysis for protein

- Symptom assessment (NCI CTCAE v.4)
- Blood samples and urine sample for biomarker analysis (see Appendix B)
- Assessment of concomitant medications
- Pregnancy test if not conducted within 3 days of starting treatment

Dispense axitinib to patient (see section 8)

7.3. DAY 1 WEEK 3

The following investigations should be conducted on day 1 of week 3 (+/- 72hrs):

- Physical examination including ECOG performance status, body weight, temperature, blood pressure, heart rate, respiratory rate

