19.3.10. TRANSLATIONAL SAMPLE SCHEDULE

Visit/Assessment	Within 21 days prior to registration	Pre-treatment day 1 week 1	Day 1 week 9	Disease progression
Percutaneous image guided biopsy of non-necrotic region of primary renal tumour (5 cores, 1 to be sent to pathology for paraffin embedding, 4 to be snap frozen in liquid nitrogen and stored at -80°C)	X		X	
Percutaneous image guided biopsy of one metastatic site (up to 5 cores to be snap frozen in liquid nitrogen and stored at -80°C) (OPTIONAL).	X			
Percutaneous image guided biopsy of site of progression, or if not possible, of non-necrotic region of primary renal tumour (up to 5 cores to be snap frozen in liquid nitrogen and stored at -80°C)				X
2 EDTA tube blood samples spun down to obtain serum (serum to be stored at -80°C)		X	X	X
Urine sample (1 container to be stored at -80°C)		X	X	X

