19.4.1. TRACKING OF BASELINE SAMPLES FOR INELIGIBLE PATIENTS

In order to minimise invasive procedures, patients will be consented for the trial prior to obtaining both the standard diagnostic biopsy sample and baseline translational study research biopsies. Patients will be asked to provide consent for the research samples to be sent to the Francis Crick Institute should histological examination of the diagnostic sample show that the patient is ineligible for A-PREDICT. Collection of these samples should be notified to the ICR Clinical Trials and Statistics Unit (ICR-CTSU) by telephoning:

[name]

09.00-17.00 (UK time) Monday to Friday

The following information will be required:

- Centre name

Version 9 Dated 02/06/2020

- Confirmation of written informed consent
- Patient's gender
- Patient's date of birth

This notification will allow these samples to be tracked by the Francis Crick Institute and ICR-CTSU.

19.5. EXPEDITED REPORTING OF FRESH TUMOUR TISSUE COLLECTION, PLANNED NEPHRECTOMY OR OTHER PALLIATIVE SURGICAL PROCEDURES

All participating sites must notify ICR-CTSU at least one week in advance of the date of planned nephrectomy or other palliative surgery.

Centres should notify ICR-CTSU of the planned procedures detailed above, by completing the A-PREDICT expedited notification of tissue collection form (included in laboratory manual) and faxing it to:

[name]

For the attention of the A-PREDICT Trial team

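### SAE reporting opens at registration, so in the available text serious complications of the mandatory baseline biopsy in the 0 to 21 days before it carry no reporting duty

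*Combined protocol and SAP*

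**What the plan says.** Section 9.5 fixes both ends of the SAE window: "Any SAE that occurs from the time of registration and up to 28 days following the last dose of axitinib must be reported". Reports are due to the trials unit within 24 hours of the site becoming aware.

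Section 7.1.1 lists, among the pre-registration procedures, "Mandatory percutaneous biopsy of non-necrotic region of primary renal tumour under ultrasound or CT guidance". It adds a biopsy of one metastatic site where possible. The sample schedule in 19.3.10 puts both under the column "Within 21 days prior to registration".

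Consent comes earlier still. Section 6.1 says: "Consent should be obtained before any trial specific assessments prescribed by the protocol are performed". Section 19.4.1 is specific to the biopsies: "patients will be consented for the trial prior to obtaining both the standard diagnostic biopsy sample and baseline translational study research biopsies".

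Section 9.1 defines an SAE by reference to a 28-day period around receipt of study drug. Sections 9.2 and 9.3 ask only whether an event is related to the drug. Section 9.9 limits the annual report's event listing to related events.

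**The concern.** The protocol requires an invasive procedure in consented patients, yet its SAE rule starts only at a later administrative step. A serious complication between biopsy and registration falls before the window. For a biopsied patient found ineligible, or not registered for any other reason, the window never opens.

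At stake is the safety record of the biopsy programme. The later scheduled biopsies do not share the problem. The week-9 biopsy is taken on study, and a progression biopsy one week after stopping axitinib falls within the 28-day tail (7 is less than 28). The baseline biopsies are therefore the only scheduled trial biopsies with an interval outside the window. A reader of the final SAE tables could take them to cover every trial biopsy.

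**Working it through.** The documents state no figure to reproduce. The check compares time windows and then looks for any other provision that covers the interval.

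**Length of the uncovered interval.** Let B be the days from biopsy to registration, T the days from biopsy to first dose, and R the days from registration to first dose, with R at least 0. Then B = T − R.

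| Source | Constraint | Resulting B |
|---|---|---|
| 7.1.1 and 19.3.10 | B between 0 and 21 | 0 to 21 days |
| Trial Summary | T at most 14, before registration | 14 − R at most, so 0 to 14 days |
| 7.13, footnote 2 (if possible) | T about 7 | 7 − R, so 0 to about 7 days |

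Section 6.2 asks for registration close to the planned start, which makes R small. With T about 7 this puts B near 7, not near 0. Every reading shortens the interval and none closes it. The Trial Summary's 14 days before treatment and the 21 days before registration in 7.1.1 and 19.3.10 also differ from each other and must be reconciled.

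**Number of procedures.**
- Primary-tumour biopsies in registered patients: 99 planned × 1 = 99.
- Of these, needed for the trial alone: between 0 and 99. Sections 7.1.1 and 19.3.1 also use the biopsy for diagnosis where histology is lacking, and the split is not given.
- Optional metastatic biopsies: 0 to 99.
- Biopsied patients never registered: number not given.

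**Does another provision cover the interval?**
- *Section 9.1.* The 28-day wording is ambiguous and might be read to include days before the first dose. Even so, 9.5 still opens at registration, and a patient who is never dosed is outside the definition on either reading.
- *Section 12.2.* It makes the investigator responsible for prompt SAE reporting without naming a start date. It relies on the definition in 9.1, so it adds no cover.
- *Screening log (5.6).* It lists four items: date identified, "Screening outcome (patient approached/ineligible/accepted participation/declined participation"), reasons for not approaching or declining, and Trial ID. None records an adverse event.
- *Sample notification (19.4.1).* It lists four items: centre, consent, gender and date of birth. None records an adverse event. Together: 0 of 4 + 0 of 4 = 0 of 8.
- *Routine checks.* Section 7.1.1 includes "Baseline symptom assessment (NCI CTCAE v.4"), an examination and blood tests, and 7.2 repeats most of these on day 1. They may record a lasting complication. But 7.1.1 does not place them after the biopsy, the day-1 set is required only "unless conducted within previous 7 days as part of pre-registration assessments", and neither carries the 24-hour duty. Patients who are not registered do not reach day 1.

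**The case against.** The strongest reply is that this is a deliberate scope. Section 9 is built around the drug: adverse events are defined in people given a medicinal product, causality is to the trial drug, and expectedness is judged against the SmPC. Within that framework, opening at registration is already earlier than first dose. This stands as a description of the design, and no passage requires a consent-based start. It does not explain why a mandatory invasive procedure is left out.

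Second, the contrast with week 9 can be overdrawn. Serious events after that biopsy are reportable, but nothing in 9.2 to 9.9 marks them as biopsy harms, and an event judged unrelated to the drug drops out of the annual report's event listing. This stands, and it means that moving the start date alone would be an incomplete remedy.

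Third, section 10.3 has the committee review safety data about every six months, and the contents of its reports are not listed. A reader might infer that the committee would learn nothing of baseline biopsy harm. The documents do not support that: the routine checks could bring some of it to light. What is missing is systematic SAE reporting.

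Fourth, the point may be overtaken by events. The protocol is Version 9, dated 02/06/2020. Section 7.7 provides for patients beyond six years on treatment, and 8.18 for those still treated after November 2018. This suggests that baseline biopsies may be complete, though no passage says that recruitment has closed.

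Finally, the biopsy is partly diagnostic, so not all of its risk is imposed by the trial. That also stands, although 7.1.1 makes it mandatory whether or not histology is already confirmed, and under 19.3.1 four of the five cores are frozen for research.

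**Conclusion.** The point holds, as a gap in the safety-reporting rule. In the available text, no SAE duty applies to a serious baseline-biopsy complication in the 0 to 21 days before registration (0 to 14, or 0 to about 7, on the shorter readings), or at any time in a biopsied patient who is never registered. Complications that arise after registration are covered.

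Three stronger readings are tempting and not supported:
- *A biased efficacy result.* The primary endpoint, sample size and two-stage decision rule do not depend on when SAE reporting opens.
- *Patients vanishing from the record.* An unregistered patient can still appear in the screening log or the sample notification. It is the event that may go unreported.
- *Selective loss of the worst cases.* A complication could in principle make a patient fail the performance status, haemoglobin or renal criteria in 5.3, but that is an inference from the criteria and no such case is documented.

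The number of events affected is unknown, because no biopsy complication rate is given. The conclusion assumes that nothing in Figure 3, the SAE form, the laboratory manual, the guidance notes or the site agreements imposes an earlier start; none of these could be checked. Confidence is medium.

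**What to change.** 1. In 9.5, start SAE reporting at consent or the first trial-specific procedure, limited before registration to SAEs related to trial procedures.
2. Include consented patients who are biopsied but not registered. They have no Trial ID under 6.2, so use a screening identifier alongside the 19.4.1 notification.
3. Clarify the SAE definition in 9.1 so that it matches this window.
4. Add a trial-procedure relatedness category in 9.2 and 9.3 and carry it through 9.6 and 9.9, so that biopsy events at baseline and week 9 can be identified as such.
5. Reconcile the biopsy timing in the Trial Summary with 7.1.1 and 19.3.10.

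The cost is edits to those sections, small form changes, a data route for unregistered patients, and a few extra screening-period reports. If recruitment has closed, the cost is one sentence in any report of biopsy safety, stating that pre-registration biopsy SAEs were not systematically collected.

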9.6. REVIEW OF SERIOUS ADVERSE EVENTS

The Chief Investigator (or designated representative) will assess all reported SAEs for causality and expectedness.

NB. The Chief Investigator cannot down-grade the Principal Investigator's assessment of causality.

Version 9 Dated 02/06/2020

SAEs assessed as having a causal relationship to study drug and as being unexpected (SUSARs) will undergo expedited reporting to the relevant authorities by ICR-CTSU (see figure 3 for SAE reporting).

Centres should respond as soon as possible to requests from the Chief Investigator or designated representative (via ICR-CTSU) for further information that may be required for final assessment of the SAE.

All reported SAEs and follow up information will be forwarded to Pfizer upon receipt at ICR-CTSU.

9.7. EXPEDITED REPORTING OF SUSARS

If an SAE is identified as being a SUSAR by the Chief Investigator, and is fatal or life threatening, it will be reported by ICR-CTSU to the MHRA, the Main REC, the sponsor institutions and Pfizer within 7 days of being notified of the event.

If an SAE is identified as a SUSAR by the Chief Investigator, and is not fatal or life threatening, it will be reported by ICR-CTSU to the MHRA, the Main REC, the sponsor institutions and Pfizer within 15 days of ICR-CTSU being notified of the event.

ICR-CTSU will report any additional relevant information to the MHRA, Main REC, the sponsor institutions and Pfizer as soon as possible, or within 8 days of the initial report of a fatal/life threatening SUSAR.

The Principal Investigators at all actively recruiting centres will be informed of any SUSARs occurring within the trial at regular intervals.

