5. PATIENT SELECTION & ELIGIBILITY

5.1. NUMBER OF PATIENTS

The aim is to recruit 99 participants.

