The following investigations should be conducted on of day 1 (+/- 72 hrs) of each 4-weekly visit.

- Physical examination including ECOG performance status, body weight, temperature, blood pressure, heart rate, respiratory rate
- Haematology, coagulation, glucose, renal and liver function, serum calcium and LDH
- Urinalysis
- Serum Thyroid Function Tests (Free T4 and TSH) should be conducted every 8 weeks from day 1 week 13
- Symptom assessment (NCI CTCAE v.4)
- Assessment of compliance with study medication (see section 8)
- Assessment of concomitant medications

Dispense axitinib to patient (see section 8)

After six years on treatment, the above investigations and assessments should be conducted every 12 weeks.

In addition, on day 1 week 17, day 1 week 25, and 12 weekly thereafter:

- CT thorax, abdomen and pelvis and assessment of response according to RECIST 1.1 criteria.

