8.9. DURATION OF THERAPY

In the absence of unacceptable toxicity treatment should continue until the patient is no longer deriving clinical benefit.

Patients may also discontinue protocol treatment in the following instances:

- Intercurrent illness which would in the judgment of the investigator affect patient safety, the ability to deliver treatment or the primary study endpoints
- Request by patient

Patients for whom treatment is discontinued should be followed for disease progression and for survival thereafter according to the Schedule of Assessments (see section 7).

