8.18. COMMERCIAL SUPPLY

After November 2018 A-PREDICT participants still receiving axitinib will be transferred to free of charge commercial supply. Commercial supply will be provided by Pfizer until A-PREDICT participants' treatment discontinuation.

Commercial supply axitinib will be labelled by the local site's pharmacy prior to dispensing in accordance with the MHRA approved A-PREDICT commercial supply label contents. Axitinib should be stored as per section 8.16 of the protocol.

Pfizer are responsible for distribution of commercial supply axitinib to participating sites.

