9.9. ANNUAL REPORTING OF SERIOUS ADVERSE REACTIONS

An annual report will be provided to the MHRA and the Main REC by ICR-CTSU and copied to the sponsors at the end of the reporting year. This will be defined as the anniversary of the date when the Clinical Trials Authorisation (CTA) was obtained. This will include all related events reported on SAE forms, and a report from the Independent Data Monitoring and Steering Committee (IDMSC).

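### Section 9.7 promises SUSAR information to investigators at recruiting centres, with no visible commitment to centres that have closed to recruitment but still treat patients

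*Combined protocol and SAP*

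**What the plan says.** Section 9.7 sets out who hears about a SUSAR. Fatal or life-threatening cases go to the regulator, the main ethics committee, the sponsor institutions and the manufacturer within 7 days. For other cases, "it will be reported by ICR-CTSU to the MHRA, the Main REC, the sponsor institutions and Pfizer within 15 days of ICR-CTSU being notified". Site investigators appear in one sentence only: "The Principal Investigators at all actively recruiting centres will be informed of any SUSARs occurring within the trial at regular intervals". The interval is not specified.

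Other sections fix how long patients may be exposed and how long events stay reportable:

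- Recruitment (5.1): "The aim is to recruit 99 participants".
- Treatment duration (8.9): "In the absence of unacceptable toxicity treatment should continue until the patient is no longer deriving clinical benefit".
- Long-term visits (7.7): "After six years on treatment, the above investigations and assessments should be conducted every 12 weeks".
- Long-term supply (8.18): "After November 2018 A-PREDICT participants still receiving axitinib will be transferred to free of charge commercial supply". The same section continues that supply until treatment stops.
- SAE window (9.5): "Any SAE that occurs from the time of registration and up to 28 days following the last dose of axitinib must be reported".

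The protocol in hand is Version 9, dated 02/06/2020.

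**The concern.** The commitment in 9.7 is triggered by whether a centre is recruiting. The need for the information is set by whether a centre is treating. The two coincide early in the trial and separate later, because recruitment has a target number and treatment has no end date.

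What is at stake is the information available to the person responsible for an exposed patient. Under 9.2 the Principal Investigator assesses the causality of each SAE, and under 12.2 takes urgent safety measures. Section 8.4 directs sites to the current SmPC when attributing an adverse event to the drug. By the definition in 9.1, however, a SUSAR is a reaction that the SmPC does not list, so the SmPC cannot stand in for a SUSAR notice until it is updated. An investigator at a centre closed to recruitment could therefore assess a second, similar event without having been told of the first.

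**Working it through.** No arithmetic applies, and the plan states no figure to reproduce. The check is to set the sections side by side.

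**Step 1. Who is promised safety information?**

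- 9.6: the trials unit makes expedited reports to the relevant authorities, with a pointer to Figure 3. All SAE reports and follow-up are forwarded to the manufacturer. Site investigators are not named as recipients.
- 9.7: regulator, main ethics committee, sponsor institutions and manufacturer; then Principal Investigators at recruiting centres.
- 9.9: "An annual report will be provided to the MHRA and the Main REC by ICR-CTSU and copied to the sponsors". Site investigators are not listed.
- 11.2: reports of the independent committee go to the Trial Management Group and, if required, to the ethics committee and regulator. The committee may also release side-effect data to that group and, if appropriate, to participants.
- 11.1: Principal Investigators may be invited onto the Trial Management Group as appropriate. Membership of every centre's investigator is not promised.

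Only the 9.7 sentence is a direct commitment to inform site investigators of SUSARs.

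**Step 2. When does that commitment lapse?**

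A centre leaves the named group when it stops recruiting. All centres leave it when the trial stops recruiting, at 99 patients (5.1) plus any replacements made on the independent committee's advice (10.3). From then on the set of actively recruiting centres is empty.

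**Step 3. Can SUSARs and exposed patients still exist at that point?**

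Yes, on the protocol's own terms. Section 8.9 ties the end of treatment to loss of clinical benefit or toxicity, not to a calendar date. Section 7.7 plans visits after six years on treatment, and 8.18 plans supply after November 2018. Section 9.5 keeps SAEs reportable until 28 days after the last dose, so a SUSAR can arise while any participant remains on axitinib.

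**Step 4. Combine.**

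After recruitment closes there may be treating centres and reportable events, while the group named in 9.7 has no members. The commitment as written then covers no treating centre, and no other visible section fills the gap.

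**What cannot be worked out.** The documents give no accrual period, no closing date for recruitment, no count of patients on long-term treatment and no expected SUSAR rate.

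**The case against.** Four points can fairly be made on the other side.

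1. **The sentence does not exclude anyone.** A reader might infer that SUSARs go exclusively to recruiting centres and that other investigators receive nothing. The documents do not support that. Section 9.7 makes a positive promise to one group and is silent on the rest, and the trials unit may well inform every centre in practice. This stands: the gap is a missing commitment, not a prohibition.

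2. **Figure 3 is not shown.** Section 9.6 points to it for SAE reporting, and it may name further recipients. Its absence from the text available is not a fault of the plan. This also stands, so the finding is limited to what is visible. If the figure does include treating centres, it and the 9.7 sentence would need to be brought into line.

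3. **Other channels exist.** Section 10.3 has the independent committee reviewing safety data about every six months, and 11.2 lets it release side-effect data. Some Principal Investigators sit on the Trial Management Group, sites use the current SmPC, and site contracts and guidance notes (12.2) are not visible here. These channels soften the concern, but those that can be seen are discretionary or partial, and none is a SUSAR notice to each treating investigator.

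4. **The effect on decisions is not shown.** A reader might infer that dose decisions would go wrong. Sections 8.4 to 8.6 base dose modification chiefly on the individual patient's own toxicity, blood pressure and proteinuria. The Chief Investigator or a delegate assesses every SAE centrally for causality and expectedness (9.4, 9.6). The documents do not show that any particular dosing decision would change.

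**Conclusion.** The point holds as a wrong trigger in a stated rule. Section 9.7 makes SUSAR notice to investigators depend on recruitment, while the protocol itself plans for treatment and SAE reporting that can outlast recruitment. No visible section commits to informing Principal Investigators at closed centres that still have patients on axitinib. The conclusion assumes that Figure 3 and the unseen site documents do not already supply that commitment.

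No size can be attached. It is tempting to state how many years a patient would spend outside the rule, but any such figure needs an assumed accrual period, and the documents give none. Sections 7.7 and 8.18 show that long-term treatment is provided for; they do not show how many patients reach it.

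The reporting deadlines to the regulator and ethics committee are unaffected, as are the two-stage design, the sample size and the primary analysis. This is a correction to safety-reporting wording, worth making because it concerns patients on treatment and is easily made.

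**What to change.** In 9.7, redefine the investigators to be informed as those at all centres that are open to recruitment, or that have a participant receiving axitinib or within 28 days of the last dose. This matches the recipient list to the SAE window in 9.5 and keeps it in force until the last participant leaves that window. Check Figure 3 against the new wording and align it if needed.

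The cost is a one-phrase amendment and a slightly wider mailing list. No dose, visit, patient procedure or analysis changes.
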